Serum antibody titers are the most common immune responses measured in vaccine studies. Serum HI antibody titers induced by the inactivated influenza virus vaccine correlates with protection (18, 19). Several studies have been conducted to evaluate the safety and immunogenicity of IIV in adults. For instance, the study by *Jackson et al* (2010) showed that IIV is immunogenic in healthy adults aged 18-49 years (20). Another study in healthy adults aged 18-48 years by Ohmit et al (2008) found a  $\geq$  4-fold increase in haemagglutination-inhibition antibody titer to influenza viruses i.e. 76.5% of subjects to the H3N2 vaccine strain, 74.7% to the H3N2 variant that circulated in 2005-2006 (p<0.001), 51.6% to the A/H1 vaccine strain (p<0.001), and 57.2% to the type B vaccine strain (15). Moreover, IIV also appeared to be well-tolerated and induced immune responses in children. (21-26).

A large population-based study in the US assessed the safety of IIV in 251,600 children aged <18 years during 1993-1999. This study did not find any increase in adverse events following vaccination with IIV (27). Another study among 791 healthy children aged 1-15 years found that 12% of vaccine recipients developed post vaccination fever (27). It was mild and self-limited.

From phase I/II trial of Tri Fluvac vaccine, 382 volunteers were screened for eligibility, out of which only 300 were enrolled. Out of the 300, 200 volunteers were given the vaccine while 100 VED volunteers were given placebos. Our results revealed that 30/100 placebo volunteers and 69/200 VED vaccine volunteers had experienced at least one adverse effect. There were altogether 34 cand 55 MMITTEE events reported in placebo and vaccine groups, respectively. Of all the 129 events 122 events were call medicine reported to not be related with the investigational products. Two events in the vaccine group IVERSITY

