# 8.7 Relationship to test vaccine (Did the test vaccine cause the adverse experience?):

The determination of the likelihood that the test vaccine caused the adverse experience will be provided by an investigator who is a qualified physician. The investigator's signed/dated initials and date on the source document or worksheet, that supports the causality noted on the AE form, ensures that a medically qualified assessment of causality was done. This initialed document must be retained for the required regulatory time frame. The criteria below are intended as reference guidelines to assist the investigator in assessing the likelihood of a relation the between the test vaccine and the adverse experience based upon the available information.

FACULTY OF TROPICAL MEDICINE MAHIDOL UNIVERSITY An adverse event's relationship to study medication assessment must be made by a medically qualified principal investigator or sub-investigator. The principle investigator or sub-investigator making relationship assessment must document this assessment in the subject's chart or file. The assessment of Causality is reported according to the investigator's best clinical judgment.

- "Related" should be selected if there is evidence of exposure to the test vaccine and the temporal sequence of the AE onset relative to administration of the test vaccine is reasonable. The AE is more likely explained by the test vaccine than by another cause. The AE shows a pattern consistent with previous knowledge of the test vaccine or test vaccine class. Or the AE could have been due to another equally likely cause.
- "Not related" should be selected if the subject did not receive the test vaccine OR temporal sequence of the AE onset relative to administration of the test vaccine is not reasonable OR there is another obvious cause of the AE. OR there is another more likely cause of the AE.
- "Not related" should be selected for subject's with accidental overdose without an associated AE.

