# **11.4 Analysis of Safety Endpoints**

The safety profile of the GPO Tri Fluvac will be evaluated by the number and proportion of participants experiencing AEs by severity and relatedness to vaccination of the following five categories for all participants:

- A. Solicited local adverse events, including redness / erythema, swelling / induration, pain within 30 minutes of vaccination and over a 3-day period (Day 0-3) post-vaccination.
- B. Solicited systemic adverse events, including fever, fatigue, malaise, muscle aches, joint aches, chills, nausea, and headache within 30 minutes of vaccination and over a 3-day period (Days 0-3) post-vaccination.
- C. Unsolicited AEs occurring within 90 days post vaccination.
- D. SAEs occurring during the entire study period (Days 0-90).

Occurrences of all events will be reported and summarized according to event severity, as "any local AE", or "any systemic AE", and by relationship to administration of study product, as deemed by a blinded study clinician. Percentage of participants experiencing each reaction or event, or at least one reaction or event will be calculated along with two-sided exact 95% CIs. No statistical testing will be performed for unsolicited AEs; including SAEs. The percentage of participants with solicited AE and SAEs will be compared between vaccine and comparator groups and a two-sided p-value of 0.05 will be considered statistically significant.

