- TREF 2.4: Summary of Adverse Events Suspected to be Related to Treatment
- TREF 2.5: Summary of Adverse Events with Definitely Related and / or Severe

Illness like Influenza (ILI)

- TREF 2.6: Summary Number of Subjects with Illness like Influenza (ILI) by GPO Tri fluvac and Active Comparator Group
- TREF 2.7: Vital Sign of Illness like Influenza (ILI) by GPO Tri fluvac and Active Comparator Group
- TREF 2.8: Physical Examination of Illness like Influenza (ILI) by GPO Tri fluvac and Active Comparator Group
- TREF 2.9: Summary RT- PCR Test for Illness like Influenza (ILI) by GPO Tri fluvac and Active Comparator Group

TREF 2.1: Summary of Treatment Emergent Adverse Events by GPO Tri fluvac and Active

Comparator Group

	EVENT		C	ASE
	Tri fluvac (N = xx)	Comparator (N = xx)	Tri fluvac (N = xx)	Comparator (N = xx)
Experienced AE, n (%)				
• AE suspected to be not related to Treatment	xx(xx.xx)	xx(xx.xx)	xx(xx.xx)	xx(xx.xx)
• AE **suspected to be related to Treatment				
Experienced SAE, n (%)				
• SAE suspected to be not related to Treatment				
• SAE **suspected to be related to Treatment				

Note: - Percentage of events will be calculated from all events of AE.

- Percentage of cases will be calculated from all cases.

** suspected to be related treatment = Probably not related ,Probably related, Definitely related

TREF 2.2: Comparison of Maximum Severity Grade of Adverse Event by GPO Tri fluvac and Active Comparator Group

Severity	Tri fluvac (N = xx) n (%)	Comparator (N = xx) n (%)
Mild	xx(xx.xx)	xx(xx.xx)
Moderate		
Severe		
Life-threatening		
P-value = x.xxxx		

Note: Summary by case who had any AEs

TREF 2.3: Summary of Adverse Events Classified by MedDRA term

]	Event	Case	
System Organ Class Term (SOC)	Preferred Term(PT)	Tri fluvac (N = xx)	Comparator (N = xx)	Tri fluvac (N = xx)	Comparator (N = xx)
		n (%)	n (%)	n (%)	n (%)
		xx(xx.xx)	xx(xx.xx)	xx(xx.xx)	xx(xx.xx)

TREF 2.4: Summary of Adverse Events Related to Treatment

		Event		Case	
System Organ Class Term (SOC)	Preferred Term(PT)	Tri fluvac (N = xx)	Comparator (N = xx)	Tri fluvac (N = xx)	Comparator (N = xx)
		n (%)	n (%)	n (%)	n (%)
		xx(xx.xx)	xx(xx.xx)	xx(xx.xx)	xx(xx.xx)

Note: suspected to be related treatment = probably not related, probably related, definitely related

TREF 2.5: Summary of Adverse Events with Definitely Related and / or Severe

Study Number	Study Group	Sex	Age	Adverse Event	Start Date	Stop Date	Medication Taken	Severity	Relation	Outcome	*ILI	Serious

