Appendix 06: Listing of Adverse Event

No.	Subject Number	Seq.	Adverse Event	Start Date	End Date	AEs (hrs)	Medication taken?	Severity	Related to Study Vac	Outcome	AE- Serious ?	Date of Immunization	Study Group	#Day at AE started after Immunization
1														
2														
3														

Note: #Day at AE started after immunization date will be calculated from date of immunization to date at AE started.

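### SAP notes to TREF 2.1 and 2.4 count *Probably not related* adverse events as related, against the two-level rule in Protocol 8.7; TREF 2.5 selects on a level that 8.7 does not have

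*SAP*

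**What the plan says.** **SAP, section 2 (Safety Assessment).** TREF 2.1 splits AEs and SAEs into suspected not related and suspected related. A footnote marks both suspected-related rows: "suspected to be related treatment = Probably not related ,Probably related, Definitely related". The note to TREF 2.4 repeats the same three levels. The table itself is headed "Summary of Adverse Events Related to Treatment". TREF 2.5 is a listing headed "Summary of Adverse Events with Definitely Related and / or Severe", with Severity and Relation among its columns. Appendix 06 lists every event, with a column headed "Related to Study Vac".

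**Protocol 8.7.** The investigator chooses *Related* or *Not related*. *Related* covers events better explained by the vaccine, and also ties: "Or the AE could have been due to another equally likely cause". *Not related* applies, among other grounds, when "there is another more likely cause of the AE".

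**Protocol 11.4.** Events are to be summarised by severity and "by relationship to administration of study product, as deemed by a blinded study clinician".

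**Protocol 6.2.** A serious outcome judged definitely related to the vaccine can lead to early termination of the trial. This is the only other place where that degree of certainty matters.

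Neither document maps the SAP's levels to those of 8.7.

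**The concern.** The protocol draws the line between related and unrelated just below a tie, so doubtful events already fall on the related side. The SAP draws it one step lower and takes in events for which, on the plain meaning of the label, something other than the vaccine is the more likely explanation. It gives no reason.

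Relatedness is part of the planned safety summary, and Protocol 11.2 expresses the trial's safety precision in terms of vaccine-related AEs and of finding no vaccine-related SAE. Under Protocol 11.6.1 the analysis follows the data analysis plan, so the notes would be programmed as they stand. What is at stake is whether the related counts in the report mean what the protocol says they mean.

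**Working it through.** No plan figure depends directly on the relatedness cut, so the main check sets the two rules side by side. The assignments to 8.7 rest on the ordinary meaning of the SAP labels, which the SAP does not define.

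| SAP label | Under Protocol 8.7 | In TREF 2.1 and 2.4 | Agree? |
|---|---|---|---|
| Definitely related | Related | related | yes |
| Probably related | Related | related | yes |
| Tie (no SAP label) | Related | related, under whichever of the three labels it is graded | yes |
| Probably not related (another cause more likely) | Not related | related | **no** |
| Remaining level, not named in the notes | Not related | not related | yes |

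The consequence depends on the case report form. The two branches exclude each other.

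1. **Graded form.** Events graded *Probably not related* move from the unrelated to the related rows of TREF 2.1, for AEs and SAEs alike, and appear in TREF 2.4. The over-count relative to 8.7 is the number of such events that are not ties.
2. **Two-level form, as 8.7 describes.** No event can be reclassified, so the over-count is 0. But the notes name levels that were never recorded. The *Definitely Related* criterion of TREF 2.5 selects nothing, so related events that are not severe drop out of that listing.

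To see what one reclassified event would do to the plan's own safety statement, start from Protocol 11.2 and Table 3, with 630 vaccine recipients. For zero events, the upper limit of a two-sided exact 95% interval is 1 − 0.025^(1/630) = 1 − exp(−3.689/630) = 0.00584, or 0.58%. This reproduces Table 3. (The text above the table calls the limit one-sided; the value is the two-sided one, as the table is labelled.) Table 3 then gives 0.88% for one event and 1.14% for two. The limit therefore rises by 0.88 − 0.58 = 0.30 percentage points for one event and by 1.14 − 0.58 = 0.56 for two. This shows how sensitive the statement is to a single event. It does not predict how many such events there would be.

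**The case against.** The best defence is that the notes define a deliberately wide *suspected* category. The list at the head of SAP section 2 does title TREF 2.4 with that word, and the notes state the pooling openly. Protocol 8.7 calls its criteria reference guidelines and leaves causality to clinical judgment. The pooling also catches ties: with no middle level, an investigator might grade a tie as *Probably not related*, and moving that whole level to *Not related* would then under-report. Finally, no decision rests on these tables. The shells carry no p-values, assessment is blinded, the rule is common to both arms, and Appendix 06 shows relatedness event by event.

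Much of this stands. The point about ties shapes the remedy, and the rest limits the seriousness. It does not remove the mismatch. Clinical judgment in 8.7 is exercised between two levels. The SAP does not say that it is widening the rule, and the heading on the table itself omits *suspected*. The use of *definitely related* in Protocol 6.2 explains why someone might want TREF 2.5, but it adds no level to 8.7.

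A reader might be tempted to go further in three ways.

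- **A multiplier for the related count.** Protocol 2.4 reports "Two events in the vaccine group" (200 recipients) as suspected related, which could be scaled up to 630. The documents do not say which cut that trial used, so its count may already include *Probably not related* events. Nor do they give any number of such events to add. The same section reports 122 of 129 events as unrelated, leaving 129 − 122 = 7 over both arms, again with no stated cut.
- **A bias between the arms, or an effect on non-inferiority.** The same rule is applied blind to both arms, and the immunogenicity endpoints do not use relatedness.
- **A change to the trial's pausing rules.** The SAP notes define table categories, and nothing in Protocol 9.3 refers to them.

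**Conclusion.** The inconsistency is certain from the text. Both notes count as related a level that, on its ordinary meaning, Protocol 8.7 puts under *Not related*, and TREF 2.5 selects on a level that 8.7 lacks. One consequence or the other follows: an over-count of related AEs and SAEs relative to 8.7 with a graded form, or rules that cannot be applied with a two-level form. The documents do not show which, and the size of any over-count cannot be derived from them. Its direction is towards over-reporting, and non-inferiority is untouched. The conclusion assumes that *Probably not related* carries its ordinary meaning. It should be corrected because it alters the meaning of a planned safety summary and costs very little to put right.

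**What to change.** - In the notes to TREF 2.1 and 2.4, define related as *Related* per Protocol 8.7.
- If the case report form holds a graded scale, fix the mapping before unblinding. *Definitely related* and *Probably related* count as Related. *Probably not related* is shown on its own row and not counted as Related.
- Apply 8.7's tie rule to any event recorded as having an equally likely other cause: it counts as Related whatever its grade. The separate row keeps visible any tie that was not recorded as one.
- Select and title TREF 2.5 on *Related* and/or severe. Keep its Relation column, so that any event recorded as definitely related, which matters for Protocol 6.2, can still be seen.

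The cost is two table notes, one title with its selection rule and, for a graded form only, one extra row and a written mapping. No further data, participants or visits are needed.

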Appendix 06: Listing of Adverse Event	. 78
Appendix 07: Listing of Illness like Influenza (ILI)	. 78
Appendix 08: Listing of Concomitant Medication	. 79
Appendix 09: List of HAI Assay (Flu A H1 Antigen)	. 80
Appendix 10: List of HAI Assay (Flu A H3 Antigen)	. 80

Study Synopsis

Title: A Phase II/III Double Blinded, Randomized, Controlled, Non-inferiority trial to evaluate the Immunogenicity and Safety of Tri Fluvac, a Seasonal Trivalent Inactivated split virion Influenza vaccine, in healthy Thai subjects aged 18 – 49 years.

Protocol #: GPO Tri Fluvac Vaccine Phase II/III

Description of Study Design:

This is a phase II/III, non-inferiority double-blinded, randomized, controlled trial of immunogenicity, safety and preliminary efficacy with two groups of participants who will received a seasonal trivalent split, inactivated influenza vaccine (A/H1N1; A/H3N2 and B) or an active comparator (licensed influenza vaccine).

A total of about 945 healthy Thai male and female adult volunteers 18 through 49 years of age; 630 participants will be randomized to receive vaccine and 315 will receive an active comparator (a 2:1 ratio) (inclusion of \sim 7% lost to follow-up).

Safety will be assessed for all participants through Day 90 after vaccination. Immunogenicity will be assessed in serum samples obtained at baseline and 21 days after vaccination in a subset of at least 630 individuals randomized to study vaccine and 315 active comparator vaccine recipients.

Study Hypothesis:

Immunogenicity: A single dose of the GPO seasonal trivalent split, inactivated influenza vaccine will induce immune responses measured by HI assay to each of the three vaccine antigens and will be non-inferior to active licensed comparator vaccine.

Safety: A single dose of the GPO seasonal trivalent split, inactivated influenza vaccine will be safe and well tolerated in adults 18 to 49 years of age.

Study Objectives:

Primary objective

Immunogenicity:

To evaluate the immunological non-inferiority seroconversion rate (using HI assay) and Geometric Mean Titre (GMT) of the GPO seasonal trivalent split, inactivated influenza vaccine compared to active comparator vaccine for each of the three vaccine antigens, three weeks after immunization (Day 21) and at the end of follow up period (Day 90).

Safety:

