Counts and percentages of subjects with solicited local and systemic reactions during the three days post-injection. In addition, all adverse events (AE) and serious adverse events (SAEs), and new onset of chronic diseases (NOCDs) will be collected for the entire study period. Specifically, the following safety parameters will be monitored and analyzed in terms of the number and proportion of participants reporting the following events will be assessed:

- Solicited local adverse events, including redness/erythema, swelling/induration, pain and limitation of arm movement within 30 minutes of vaccination and over the 3-day period post vaccination (Day 0-3).

- Solicited systemic adverse events, including fever, fatigue/malaise, muscle aches, joint aches, chills, nausea and headache within 30 minutes of vaccination and over the 3-day period post vaccination (Day 0-3).

- Unsolicited adverse events (AEs) occurring within 90 days post vaccination.

- Serious Adverse Events (SAE) occurring during the entire study period (Days 0-90).

Counts of all events will be reported and summarized according to event severity, as "any local AE", or "any systemic AE", and by relationship to administration of study product, as deemed by a blinded study clinician. Percentages of participants experiencing each reaction or event, or at least one reaction or event will be calculated along with two-sided exact 95% CIs. The percentage of participants with solicited AE and SAEs will be compared between vaccine and comparator groups and a two-sided p-value of 0.05 will be considered statistically significant.

Inferential analyses

GMT ratios (GMT active comparator vaccine/GMT GPO TRI FLUVAC) and difference of seroconversion rate (with two-sided 95% CI) related to the comparisons of interest will be computed. Acceptance value of GMT ratios at \leq 1.5 and/or difference of seroconversion rate at \leq 10% for the upper bound of the 95% CI will be considered for non-inferiority.

Secondary Immunogenicity Endpoints and analysis:

The secondary immunogenicity endpoints will be analyzed by the following:

- Number and percentage of participants with a HI antibody titer $\geq 1:40$ (seroprotective level) to each of the three vaccine antigens measured on Day 21 and Day 90.

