	Tri fluvac (N = xx)	Comparator (N = xx)	Tri fluvac (N = xx)	Comparator (N = xx)	Tri fluvac (N = xx)	Comparator (N = xx)	Tri fluvac (N = xx)	Comparator (N = xx)
Min, Max								
P- value =								

	D	Day 0 Day 7		Day 21		Day 90		
	Tri fluvac (N = xx)	Comparator (N = xx)	Tri fluvac (N = xx)	Comparator (N = xx)	Tri fluvac (N = xx)	Comparator (N = xx)	Tri fluvac (N = xx)	Comparator (N = xx)
HEENT, n (%)								
Normal	xx(xx.xx)	xx(xx.xx)						
Abnormal	xx(xx.xx)	xx(xx.xx)						
P- value =	X.2	xxxx						
Lungs, n (%)								
Normal								
Abnormal								
P- value =								
Cardiovascular, n (%)								
Normal								
Abnormal								
P- value =								
Gastrointestinal, n (%)								
Normal								
Abnormal								
P- value =								
Musculoskeletal, n (%)								
Normal								
Abnormal								
P- value =								
Skin, n (%)								
Normal								
Abnormal								
P- value =								

TREF 3.4: Physical Examination by GPO Tri Fluvac and Active Comparator Group

	Day 0		D	Day 7		Day 21		Day 90	
	Tri Fluvac (N = xx)	Comparator (N = xx)	Tri Fluvac (N = xx)	Comparator (N = xx)	Tri Fluvac (N = xx)	Comparator (N = xx)	Tri Fluvac (N = xx)	Comparator (N = xx)	
Neurologic, n (%)	X	((
Normal	xx(xx.xx)	xx(xx.xx)							
Abnormal	xx(xx.xx)	xx(xx.xx)							
P- value =	X XXXX								

TREF 3.4: Physical Examination by GPO Tri Fluvac and Active Comparator Group (Continue)

TREF 3.5: Comparison of Maximum Grade of Any Local Reaction at Post Immunization by GPC
Tri fluvac and Active Comparator Group

Grade		Tri Fluvac (N = xx) n (%)	Comparator (N = xx) n (96)
Grada 0			
Grade 0		XX(XX.XX)	XX(XX.XX)
Grade 1		XX(XX.XX)	XX(XX.XX)
Grade 2		xx(xx.xx)	xx(xx.xx)
Grade 3		xx(xx.xx)	xx(xx.xx)
P- value =	X.XXXX		

Note: - Any local reaction on any day (by case)

- Erythema and Induration will be not included.

- Grading

- Grade 0 none
- Grade 1 mild
- Grade 2 moderate
- Grade 3 severe

TREF 3.6: Comparison of Local Reaction at Post Immunization each Follow up Time by GPO Tri Fluvac and Active Comparator Group

	30	min	D	Day 1	D	ay 2	Da	ny 3
Local Reaction	Tri Fluvac	Comparator						
	(N=xx)							
- Pain, n (%)	xx(xx.x)	xx(xx.xx)						
p-value =	X.:	xxxx						
- Limitation of arm movement, n (%)								
p-value =								
- Erythema (cm.)								
n								
Mean(SD)								
Median								
Min, Max								
p-value =								
- Swelling (cm.)								
n								
Mean(SD)								
Median								
Min, Max								
p-value =								
- Induration (cm.)								
n								
Mean(SD)								

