Median								
Min, Max								
p-value =								

Note: - Summary by case who had symptoms

TREF 3.7: Comparison of Maximum Grade of Local Reaction by Symptom at Post Immunization
by GPO Tri fluvac and Active Comparator Group

Lo	ocal Reaction		Tri fluvac (N=xx)	Comparator (N=xx)
Pain,	n (%)			
Grad	de 0		xx(xx.xx)	xx(xx.xx)
Grad	de 1		XX(XX.XX)	xx(xx.xx)
Grad	de 2		xx(xx.xx)	xx(xx.xx)
Grad	de 3		XX(XX.XX)	xx(xx.xx)
	p-value =	X.XXXX		
Limi	tation of arm movemen	ıt, n (%)		
Grad	de 0			
Grad	de 1			
Grad	de 2			
Grad	de 3			
	p-value =			
Note:	- On any day (by cas	es)		
	- Grading	,		
	Grada 0 por	no		
	Grade 1 mi	le Id		
	Grade 2 mg	nderate		
	Grade 3 - set	nere		
	Grade 5 - sev			

Number of Days by Local Reaction	Tri fluvac (N = xx)	Comparator (N = xx)	
Pain			
only 30 min.	xx (xx.xx)	xx (xx.xx)	
1 day	xx (xx.xx)	xx (xx.xx)	
2 days	xx (xx.xx)	xx (xx.xx)	
3 days	xx (xx.xx)	xx (xx.xx)	
p-value = x.xxxx			
Limitation of arm movement			
only 30 min.	xx (xx.xx)	xx (xx.xx)	
1 day	xx (xx.xx)	xx (xx.xx)	
2 days	xx (xx.xx)	xx (xx.xx)	
3 days	xx (xx.xx)	xx (xx.xx)	
p-value = x.xxxx			

TREF 3.8: Comparison Number of Subject by Number of Local Reaction Days at Post Immunization GPO Tri fluvac and Active Comparator Group

Note: - Subjects who had symptom with local reaction will be considered in this table.

- Number of subjects who had symptom will be compared between Tri fluvac and comparator.

- Percentage will be calculated from total enrollment subject.

TREF 3.9: Comparison Number of Subjects by Number of Local Reaction at Post Immunization
GPO Tri fluvac and Active Comparator Group

Number of Local Reaction	Tri fluvac (N = xx)	$\begin{array}{l} \textbf{Comparator} \\ \textbf{(N = xx)} \end{array}$
No symptom	xx (xx.xx)	xx (xx.xx)
1 symptom	xx (xx.xx)	xx (xx.xx)
2 symptoms	xx (xx.xx)	xx (xx.xx)
p-value = x.xxxx		

Note: - All enrollment Subjects will be considered in this table. - Percentage will be calculated from total enrollment subject.

TREF 3.10: Comparison of Maximum Grade of Any Systemic Reaction at Post Immunization by GPO Tri fluvac and Active Comparator Group

Create	Tri fluvac	Comparator	
Grade	(N=xx)	(N=xx)	
	n (%)	n (%)	
Grade 0	xx(xx.xx)	xx(xx.xx)	
Grade 1	xx(xx.xx)	xx(xx.xx)	
Grade 2	xx(xx.xx)	xx(xx.xx)	
Grade 3	xx(xx.xx)	xx(xx.xx)	
P-value = x.xxxx			

Note: Grading

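### TREF 2.2 and the size rows of TREF 3.6 test only participants who had an event, so extra mild or small reactions can read as lower severity

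*SAP*

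**What the plan says.** **AE severity.** TREF 2.2 in the SAP is titled "Comparison of Maximum Severity Grade of Adverse Event by GPO Tri fluvac and" active comparator group. Its rows are mild, moderate, severe and life-threatening, followed by one p-value. There is no row for participants without an AE, and the note reads "Summary by case who had any AEs".

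**Reaction size.** TREF 3.6 gives erythema, swelling and induration in centimetres at 30 minutes and on Days 1, 2 and 3, as n, mean (SD), median, range and a p-value. Its note reads "Summary by case who had symptoms".

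**Other tables.** TREF 2.1 counts AE and SAE cases by relatedness, without a severity split or a p-value. TREF 3.5 grades any local reaction and has a Grade 0 row, but its note says "Erythema and Induration will be not included". TREF 3.7 grades pain and limitation of arm movement only. TREF 3.10 and 3.12 grade systemic reactions with a Grade 0 row.

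**Testing rules.** The SAP's primary safety text compares the percentages with solicited AEs and with SAEs, and says "a two-sided p-value of 0.05 will be considered statistically significant". Protocol section 11.4 says "No statistical testing will be performed for unsolicited AEs; including SAEs".

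**The concern.** Randomisation makes the arms comparable when everyone vaccinated is counted. Whether a participant has an AE or a skin reaction is settled after vaccination and may be caused by the vaccine. Restricting a test to those participants compares two groups selected by outcome.

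The bias has a predictable direction. If one vaccine causes extra mild events, they enter its denominator and dilute its moderate and severe share. If it causes extra small reactions, they lower its mean diameter. The more reactogenic vaccine can then appear significantly less severe, although no participant is better off.

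Comparing solicited symptoms, AEs and SAEs between arms is a primary safety objective. Redness and swelling/induration are named primary safety endpoints. For the three size measures, TREF 3.6 is the only table that gives each its own between-arm comparison.

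**Working it through.** **1. Which rows are affected.** With no row for participants without an AE, the TREF 2.2 p-value can only test the grade split among those who had one. A mean diameter among participants with the symptom has the same restriction. The pain and limitation lines of TREF 3.6, and every line of TREF 3.11, are different. Each is a single n (%) entry with a p-value. Restricted to people with that symptom, every entry would be 100% and nothing could be tested. There the note must mean that participants are counted, not events.

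**2. Arm sizes.** The documents give no numerical figure for TREF 2.2 or 3.6. The 630:315 split comes from the H3 seroconversion calculation, which reproduces: n(comparator) = (1.960 + 0.842)² × 0.535 × 0.465 × (1 + 1/2) / 0.10² = 292.9, so 293, and 586 for Tri Fluvac. Dividing by 0.93 gives 315.1 and 630.1, against the planned 315 and 630.

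**3. Anchor for event rates.** Protocol section 2.4 reports at least one adverse effect in "30/100 placebo volunteers and 69/200" vaccine volunteers, that is 30.0% and 34.5%, a gap of 4.5 points. In the placebo arm 4/100 were moderate and 1/100 severe. In the vaccine arm 2/200 were severe. The licensed comparator's rates are not given, so what follows is assumption with a range.

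**4. Simulation for TREF 2.2.** Both arms have 4% moderate and 1% severe, and the comparator has 25% mild. Tri Fluvac adds x points of mild events only, so its mild share among cases is (25 + x)/(30 + x), against 25/30 = 83.3%. The shell names no test, so Pearson chi-square at 0.05 is assumed for the restricted table. The rank test uses all participants, with none as the lowest category. Separate runs of 4,000 to 20,000 trials at 630 vs 315 agree to within about two points.

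| Added mild points | Mild share among cases, Tri Fluvac | Restricted test significant in favour of Tri Fluvac | All-participant rank test significant against Tri Fluvac |
|---|---|---|---|
| 0 | 83.3% | 3% | 2% |
| 4.5 | 85.5% | 6–7% | not run |
| 10 | 87.5% | 15–17% | 82% |
| 20 | 90.0% | 37–38% | 100% |
| 30 | 91.7% | 57–58% | 100% |

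With more moderate and severe events (8% and 2% in both arms, comparator mild 20%), the restricted test favours Tri Fluvac in 29%, 68% and 89% of trials at 10, 20 and 30 added points.

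**5. One worked table.** Take that second set with 20 added points. Expected counts (mild, moderate, severe) are 252, 50, 13 of 630 for Tri Fluvac and 63, 25, 6 of 315 for the comparator.
- Among cases, the mild share is 252/315 = 80.0% against 63/94 = 67.0%, p = 0.031, apparently favouring Tri Fluvac.
- Among all vaccinated, any AE is 315/630 = 50.0% against 94/315 = 29.8%, p < 0.0001 against Tri Fluvac.
- Moderate or worse is 63/630 = 10.0% against 31/315 = 9.8%, p = 0.94.

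**6. Reaction size.** Assume typical reactions of 3 cm (SD 1) in both arms and extra Tri Fluvac reactions of 1 cm (SD 0.4). With comparator incidence 2.5% and an extra 2.5% in Tri Fluvac, a Welch t-test among reactors favours Tri Fluvac in 57% of trials. With 5% and an extra 5% it does so in 88%. A rank test on everyone, with 0 cm for non-reactors, goes against Tri Fluvac in 42% and 73%. For scale, the phase I/II swelling rates were 2.5% (vaccine) and 2% (placebo).

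**The case against.** **Much of the reactogenicity reporting is already sound.** Grade 0 rows appear in TREF 3.1, 3.2, 3.5, 3.7, 3.10 and 3.12. This stands. A reader might infer from the shared note that TREF 3.11 and the pain and limitation rows of TREF 3.6 are restricted too. Step 1 shows that reading does not work, and TREF 3.7 and 3.12 compare those symptoms in everyone.

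**The text plans all-participant reporting.** Protocol section 11.4 evaluates AEs by severity as proportions of all participants, and both documents plan exact 95% CIs. TREF 2.1 and the AE figures show the number of cases, so a careful reader would see a large excess beside TREF 2.2. This stands as mitigation, but no table shell puts severity on that denominator.

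**TREF 2.2 is not the stated inferential comparison.** That comparison is the percentage with solicited AEs and with SAEs, and the protocol bars testing of unsolicited AEs. This is correct. It is a further reason to remove or reconcile the p-value, because TREF 2.2 does not say that it leaves unsolicited AEs out.

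**A large distortion needs a large excess.** The comparator is a licensed split-virion vaccine with the same HA content per strain, and even against placebo the phase I/II gap was 4.5 points. A reader might picture any AE at 40% against 20% with 5% severe in both arms. Among cases that gives 32/252 against 16/63, Fisher p = 0.018, and among all vaccinated 32/630 against 16/315, p = 1.0. The arithmetic is right, but nothing in the documents supports a doubled rate or 5% severe.

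**Conclusion.** The point holds for two items: TREF 2.2, and the erythema, swelling and induration rows of TREF 3.6. Their p-values compare groups selected by a post-vaccination outcome and can favour the vaccine that adds mild or small reactions. No other SAP table compares AE severity, or these sizes, in all vaccinated participants. TREF 3.5 does not name swelling among its exclusions, but even if swelling is included there it is merged into any local reaction.

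For TREF 2.2 the risk is modest at the phase I/II gap and substantial only if the excess of mild events is large. It would be too strong to say that a misleading result is likely. The sizes rest on assumed rates and assumed tests, and the reaction-size figures have the least support because the documents give no diameters. Neither the solicited symptoms graded with a Grade 0 row nor the immunogenicity conclusions are affected.

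**What to change.** - **TREF 2.2:** add a no-AE row, use all vaccinated participants as denominator, and state whether the table covers solicited AEs, unsolicited AEs or both.
- **TREF 3.6, size measures:** report erythema, swelling and induration as n/N vaccinated and by the Appendix A grade, with Grade 0 for none. Where diary data are missing, show the number contributing. Appendix A's Grade 1 starts at 2.5 cm, so keep the any-reaction n/N beside the grades and state how smaller reactions are classified.
- **Subset p-values:** drop them, or keep the among-cases severity and diameter summaries as descriptive and label them so. Removing the TREF 2.2 p-value also reconciles it with protocol section 11.4.
- **TREF 3.6 and 3.11 notes:** reword them to say that participants are counted and that the denominator is all vaccinated participants.

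The cost is a change to table shells and code. Diameters are already measured by ruler and Appendix A already grades them, so no new data are needed.
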